14.2 Serious adverse event

An adverse event should be classified as a serious adverse event (SAE) if it meets one of the following criteria:

Fatal	Adverse event results in death.
Life threatening	The adverse events placed the subject at immediate risk of death. This classification did not apply to an adverse event that hypothetically might cause death if it were more severe.
Hospitalization	It required or prolonged inpatient hospitalization. Hospitalizations for elective medical or surgical procedures or treatments planned before enrollment in the treatment plan or routine check-ups are not SAEs by this criterion. Admission to a palliative unit or hospice care facility is not considered to be a hospitalization.
Disabling/incapacitating	Resulted in a substantial and permanent disruption of the subject's

	ability to carry out normal life functions.
Congenital anomaly or birth defect	An adverse outcome in a child or fetus of a subject exposed to the molecule or treatment plan regimen before conception or during pregnancy.
Medically significant	The adverse event did not meet any of the above criteria but could have jeopardized the subject and might have required medical or surgical intervention to prevent one of the outcomes listed above.

14.3 Unexpected adverse event

An unexpected adverse event is defined as an event that has a nature or severity, or frequency that is not consistent with the applicable investigator brochure; or, for the purposes of IRB reporting, not consistent with the prior medical condition of the subject or other treatment given to the subject. “Unexpected,” as used in this definition, refers to an adverse drug experience that has not been previously observed and reported in preclinical or clinical studies rather than an experience that has not been anticipated based on the pharmacological properties of the study drug.

14.4 Monitoring and recording adverse events

Grade 3 and above adverse events (or highly unusual grade 2 adverse events) and all SAEs that occur during the AE monitoring period (see section 14.7) will be followed and captured in the database. When a grade 3 adverse event increases in severity to grade 4 or above, the event will be captured at its highest grade. Clinically significant AEs beyond the AE monitoring period may also be captured at the discretion of the investigator. When a subject goes on to further treatment off protocol, adverse events will no longer be collected with the exception of death. The investigator should attempt to establish a diagnosis of the event on the basis of signs, symptoms and/or other clinical information. In such cases, the diagnosis should be documented as the adverse event and/or serious adverse event and not described as the individual signs or symptoms. The following information should be recorded:

- Description of the adverse event using concise medical terminology.
- Description as to whether or not the adverse event is serious, noting all criteria that apply.
- The start date (date of adverse event onset).
- The stop date (date of adverse event resolution).
- The maximum severity (grade) of the adverse event.
- A description of the potential relatedness of the adverse event to study drug, a study procedure, or other causality.
- The action taken due to the adverse event.
- The outcome of the adverse event.

14.5 Grading adverse event severity

All adverse events will be graded in severity according to the NCI Common Terminology Criteria for Adverse Events (CTCAE) Version 5.0. A copy of the CTCAE v5.0 can be downloaded from the CTEP home page (https://ctep.cancer.gov/protocolDevelopment/electronic_applications/ctc.htm#ctc_50). If a

CTCAE criterion does not exist, the investigator should use the grade or adjectives: Grade 1 (mild), Grade 2 (moderate), Grade 3 (severe), Grade 4 (life-threatening), or Grade 5 (fatal) to describe the maximum intensity of the adverse event.

14.6 Attribution of an adverse event

Association or relatedness to the study agent will be assessed by the investigator as follows:

- Definite: The event follows a reasonable temporal sequence from exposure to the investigational agent, has been previously described in association with the investigational agent, and cannot reasonably be attributed to other factors such as the subject's clinical state, other therapeutic interventions or concomitant medications; AND the event disappears or improves with withdrawal of the investigational agent and/or reappears on re-exposure (e.g., in the event of an infusion reaction).
- Probable: The event follows a reasonable temporal sequence from exposure to the investigational agent and has been previously described in association with the investigational agent OR cannot reasonably be attributed to other factors such as the subject's clinical state, other therapeutic interventions or concomitant medications.
- Possible: The event follows a reasonable temporal sequence from exposure to the investigational agent but could be attributable to other factors such as the subject's clinical state, other therapeutic interventions or concomitant medications.
- Unlikely: Toxicity is doubtfully related to the investigational agent(s). The event may be attributable to other factors such as the subject's clinical state, other therapeutic interventions or concomitant medications.
- Unrelated: The event is clearly related to other factors such as the subject's clinical state, other therapeutic interventions or concomitant medications.

For general adverse event assessment, an adverse event is considered related if it is assessed as definitely, probably, or possibly related; unrelated if it is assessed as unlikely related or unrelated.

14.7 Adverse event reporting period

Adverse events will be tracked for up to 56 days after the last dose of CPX-351 or until resolution. Collection of AEs should cease with the start of any new therapy or conditioning for transplant.

14.8 Adverse event reporting requirements

The Principal Investigator will report adverse events to the FHCRC IRB in accordance with IRB policies, including expedited reporting of serious adverse events that are related or possibly related to the research and unexpected as defined by the IRB.

The Sponsor-Investigator assumes responsibility for IND safety reporting to the FDA in accordance with regulations under 21 CFR 312.32, including notifying FDA of any serious, unexpected, suspected adverse reaction (SUSAR) within 15 calendar days (or 7 days in the event of a fatal or life-threatening SUSAR) after determining that the information qualifies for reporting. Serious adverse events not meeting criteria for reporting as SUSARs will be reported in the annual report to the IND as required by 21 CFR 312.33.

The PI (or designee) must send all SAEs (initial and follow-up) that require collection and reporting per protocol, and which occur in a subject who received a Jazz Pharmaceuticals product as study drug, to the JP Drug Safety Department within 1 business day of their awareness of the SAE ([contact]). The PI (or designee) will report the SAEs using a US-FDA Form 3500A (MedWatch form). [Note: the MedWatch form, is available at <http://www.fda.gov/downloads/Safety/MedWatch/HowToReport/DownloadForms/UCM082728.pdf>]. The PI (or designee) must also provide JP Drug Safety Department ([contact]) with a copy of all submissions made to the FDA at the time the submission is made. In addition, all other adverse events will be reported to the JP Drug Safety Department in summary or line-item form upon JP's request and at the conclusion of the study.

15.0 DATA AND SAFETY MONITORING PLAN

Institutional support of trial monitoring will be in accordance with the FHCRC/University of Washington Cancer Consortium Institutional Data and Safety Monitoring Plan. Under the provisions of this plan, FHCRC Clinical Research Support (CRS) coordinates data and compliance monitoring conducted by consultants, contract research organizations, or FHCRC employees unaffiliated with the conduct of the study. Independent monitoring visits occur at specified intervals determined by the assessed risk level of the study and the findings of previous visits per the institutional DSMP.

In addition, protocols are reviewed at least annually and as needed by the Consortium Data and Safety Monitoring Committee (DSMC), FHCRC Scientific Review Committee (SRC) and the FHCRC/University of Washington Cancer Consortium Institutional Review Board (IRB). The review committees evaluate accrual, adverse events, stopping rules, and adherence to the applicable data and safety monitoring plan for studies actively enrolling or treating subjects. The IRB reviews the study progress and safety information to assess continued acceptability of the risk-benefit ratio for human subjects. Approval of committees as applicable is necessary to continue the study.

The trial will comply with the standard guidelines set forth by these regulatory committees and other institutional, state and federal guidelines.

16.0 DATA MANAGEMENT/CONFIDENTIALITY

Research data will be recorded in a study-specific, password protected database using a unique study ID for each patient to assure patient confidentiality. Data from source documents will be transcribed into this database. Source documents are documents where patient data are recorded and documented for the first time. They include, but are not limited to, hospital records, clinical and office charts, laboratory notes, memoranda, quality of life assessments, pharmacy dispensing records, recorded data from automated instruments, copies of transcriptions that are certified after verification as being accurate and complete, X-rays, patient files, and records kept at the pharmacy, laboratories, and medico-technical departments involved in the clinical trial. There will be no case reports forms (CRFs) used for this trial.

The Principal Investigator will ensure that data collected conform to all established guidelines. Each subject is assigned a unique subject number to protect subject confidentiality. Subjects will not be

referred to by this number, by name, or by any other individual identifier in any publication or external presentation.

The licensed medical records department, affiliated with the institution where the subject receives medical care, maintains all original inpatient and outpatient chart documents. Patient research files will be maintained under control of the local site Principal Investigator and/or study team as designated by institutional policies.

Access to the study database will be restricted by electronic password protection and restricted access to computers per institutional policies and/or guidelines.

17.0 STATISTICAL CONSIDERATIONS

17.1 Study Design

Randomized, open-label interventional trial.

17.2 Primary/Secondary Endpoints, Objectives and Analytical Methods

The primary endpoint of the study is overall survival from the time of randomization. The survival (in days) of subjects in the two arms will be compared using the stratified log-rank test (stratified on number of chemotherapy cycles and disease risk, factors that randomization is stratified on). Patients still alive at last contact will be censored. End of study will be defined as 2 years after the last patient is randomized. The primary endpoint will be compared between groups using the intent-to-treat principle.

A secondary endpoint of the study is **relapse-free survival** (RFS) from the time of randomization, to be compared between groups with the stratified log-rank test. For descriptive purposes, we shall also report survival and RFS estimates from time of transplant among patients who receive a transplant. Patients alive without relapse at last contact will be censored for RFS.

[figure not shown]
A secondary objective of the study is to compare the **rate of transplantation** among patients with MRD following intensive chemotherapy. The proportion of patients who were transplanted will be compared between arms using the chi-square test

A secondary objective of the study is to examine the **types of transplant** received following treatment with CPX-351 as compared to patients receiving immediate transplantation. Among patients receiving transplantation, the proportion of patients in each arm receiving myeloablative transplant conditioning will be compared using the chi-square or Fisher's exact test. Among patients receiving transplantation, the proportion of receiving donor stem cells from a haploidentical donor, an unrelated donor, or from cord blood unit will be compared across arms using the chi-square or Fisher's exact test.

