3.3.2 Secondary Endpoints

- **Relapse-free survival** from the time of MRD identification and (among patients transplanted) from the time of transplantation. The following comparisons will be made: (1) number of days elapsing between the date of MRD identification and the date of death or relapse, (2) among transplanted patients, the number of days elapsing between the date of transplantation and the date of death or relapse.
- **Rate of transplantation** following treatment with CPX-351 among patients with MRD following intensive chemotherapy. The proportion of patients having begun transplant conditioning 60 days and 180 days following enrollment will be compared using the chi-squared test. The **time to transplant** among the two arms will be compared by comparing the number of days elapsed between enrollment and the initiation of transplant conditioning by the log-rank test.
- Frequencies of the **types of transplant** received. Among the patients receiving transplantation, the proportion of patients in each arm receiving myeloablative transplant conditioning will be compared using the chi-squared or Fisher's exact test. Among patients receiving transplantation, the proportion of patients in each arm receiving donor stem cells from a haploidentical donor, an unrelated donor, or from cord blood unit will each be compared using the chi-squared or Fisher's exact test.

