17.3 Sample Size and Power

Outcomes for patients with MRD following intensive chemotherapy at FHCRC since 2008 were reviewed. From these observed data, we fit piecewise exponential survival distributions and used these as the assumed-true distributions for the two arms. These assumed-true distributions are shown

in the figure below. From the observed data, the hazard of death was estimated to be 0.58 (transplant vs chemotherapy).

Estimates of power for specified sample sizes were obtained by randomly drawing survival times from each assumed-true survival distribution for the number of patients assumed for each group, resulting in “simulated” clinical trials under the assumptions depicted in the curves above. The data from this simulated trial were then compared using the log-rank test and a p-value was generated. This process was repeated 500 times, and the proportion of simulated trials that led to a p-value less than the significance level dictated by the trial provides an estimate of power to observe a statistically significant (at a two-sided significance level) difference in survival between the two groups.

Power estimates further assumed uniform accrual over 3 years with minimum follow-up of 2 years (so the longest potential follow-up would be 5 years and the minimum potential follow-up would be 2 years).

Based on the assumptions above, the estimated power for this design is summarized below for various significance levels and 65 patients/group. Power estimated from 500 simulations. The number of events required is estimated to be 107.

Alpha=.05, power ~ 89.4%

Alpha=.10, power ~ 93.8%

Alpha=.15, power ~ 94.8%

Alpha=.20, power ~ 96.4%

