17.4 Randomization

Subject randomization will be 1:1 and will be done using a permuted-block routine with random block sizes. Randomization will be stratified on two factors: number of chemotherapy cycles (1 vs. 2 courses pre-HCT) and disease risk (standard risk vs. high risk, where high-risk disease is defined based on ELN or being in CRi).

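### The transplantation rate is tested without the randomization strata that Section 17.2 uses for OS and RFS; if those strata predict reaching transplant, the test is mildly conservative and gives up a little power

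*Combined protocol and SAP*

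**What the plan says.** Section 17.4 sets the allocation: "Subject randomization will be 1:1 and will be done using a permuted-block routine with random block sizes". It continues: "Randomization will be stratified on two factors: number of chemotherapy cycles (1 vs. 2 courses pre-HCT) and disease risk". Two binary factors make four strata.

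Section 17.2 carries the strata into the survival analyses. Overall survival is "compared using the stratified log-rank test (stratified on number of chemotherapy cycles and disease risk, factors that randomization is stratified on"). Relapse-free survival is "to be compared between groups with the stratified log-rank test". (Section 3.3.1 names only a log-rank test for survival; Section 17.2 is the fuller statement.)

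The same section then turns to the transplantation rate: "The proportion of patients who were transplanted will be compared between arms using the chi-square test". Nothing restricts this to transplanted patients, so I read it as a comparison of all randomized patients. Section 3.3.2 gives a timed version, also unstratified: "The proportion of patients having begun transplant conditioning 60 days and 180 days following enrollment will be compared using the chi-squared test".

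No alpha, power, target difference or effect estimate is given for these proportions. The power figures in Section 17.3 are for survival only.

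**The concern.** When allocation is balanced within strata that predict the outcome, differences between strata contribute almost nothing to the variation of the arm difference. The ordinary chi-square test still counts them in its variance. The variance is then too large, the true size falls below the nominal level, and power that the stratified randomization made available is not collected.

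The endpoint matters for interpreting the trial. The background in Section 2.2.3 reports that only 16 of 49 patients given chemotherapy for MRD went on to transplant. Section 4.1 lists infrequent transplantation after CPX-351 as a reason to discontinue. A conservative test of a possible harm is not automatically the cautious choice, because a real reduction is somewhat more likely to be reported as non-significant.

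**Working it through.** **Plan's own figure.** There is none to reproduce for this endpoint.

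**Inputs from the documents.** Section 17.3 gives the sample size: "the estimated power for this design is summarized below for various significance levels and 65 patients/group". Section 17.4 gives four strata and 1:1 permuted blocks.

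**Assumptions.** Two-sided alpha 0.05; Pearson chi-square without continuity correction; block sizes 2, 4 and 6; both factors split 50/50; the same odds ratio (OR) for each factor, from 1 to 5; and the transplant rates shown below. The documents give no transplant rate by cycle number or disease risk, so these are ranges and not estimates.

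**Step 1: size in closed form.** Let p_s be the transplant rate in stratum s, and p the mean over four equal strata. The chi-square test uses a variance proportional to p(1 − p). With balance within strata, the actual variance is smaller by the factor 1 − R, where R = mean of (p_s − p)² ÷ [p(1 − p)]. True size is therefore approximately 2 × [1 − Φ(1.96 ÷ √(1 − R))].

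With an overall rate of about 75% and no arm difference:

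| OR per factor | Stratum rates | R | 1.96 ÷ √(1 − R) | Size, formula | Size, simulated |
|---|---|---|---|---|---|
| 2 | 0.61, 0.76, 0.76, 0.86 | 0.00797 ÷ 0.1887 = 0.042 | 2.003 | 0.045 | 0.0435 |
| 3 | 0.54, 0.78, 0.78, 0.91 | 0.01787 ÷ 0.1862 = 0.096 | 2.061 | 0.039 | 0.0393 |
| 5 | 0.45, 0.80, 0.80, 0.95 | 0.03375 ÷ 0.1875 = 0.180 | 2.164 | 0.030 | 0.0301 |

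The simulated column comes from 20,000 trials of 130 patients per row (Monte Carlo standard error about 0.0015). Formula and simulation agree within about that error.

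**Step 2: size over overall rates of 60%, 75% and 85%.** Chi-square: 0.050 to 0.053 at OR 1, 0.046 to 0.049 at OR 1.5, 0.044 to 0.048 at OR 2, 0.037 to 0.043 at OR 3, and 0.029 to 0.036 at OR 5. The Cochran-Mantel-Haenszel (CMH) test stays between 0.047 and 0.053 throughout.

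**Step 3: power, 65 per arm** (Monte Carlo standard error about 0.3 points):

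| Rates compared | OR per factor | Chi-square, % | CMH, % | Gain, points |
|---|---|---|---|---|
| 85% vs 65% | 1 | 76.61 | 76.32 | −0.29 |
| 85% vs 65% | 2 | 76.92 | 78.05 | 1.13 |
| 85% vs 65% | 3 | 77.69 | 80.33 | 2.64 |
| 85% vs 65% | 5 | 78.36 | 83.53 | 5.17 |
| 90% vs 70% | 2 | 84.16 | 84.97 | 0.81 |
| 90% vs 70% | 3 | 84.33 | 86.11 | 1.78 |
| 90% vs 70% | 5 | 84.99 | 88.67 | 3.68 |
| 80% vs 60% | 2 | 71.72 | 72.96 | 1.24 |
| 80% vs 60% | 3 | 71.98 | 75.01 | 3.03 |
| 80% vs 60% | 5 | 73.81 | 80.28 | 6.47 |

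The chi-square test does not get worse as the strata strengthen. It fails to collect a gain that CMH collects. With uneven factors (75/25 and 40/60) and 85% vs 65%, the gain is 77.70 − 76.77 = 0.93 points at OR 2 and 79.23 − 77.16 = 2.07 points at OR 3.

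**Step 4: a loss on the historical scale.** Take 16/49 = 32.7% against an assumed 80%. The pooled rate is 0.563, the null standard error √(2 × 0.563 × 0.437 ÷ 65) = 0.087, and the alternative standard error √(0.8 × 0.2 ÷ 65 + 0.327 × 0.673 ÷ 65) = 0.076. Chi-square power is Φ[(0.473 − 1.96 × 0.087) ÷ 0.076], about Φ(4), above 99.9%. The choice of test is immaterial there.

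**Step 5: continuity correction.** The plan does not say whether one is applied. With the Yates correction, size in the Step 2 runs falls to 0.016 to 0.035. Power for 85% vs 65% at OR 2 falls from 76.92% to 70.06%, a larger cost than ignoring the strata.

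**The case against.** The strongest reply is that everything depends on the strata being prognostic for transplant, and the documents neither say nor quantify that. Eligibility also narrows the variation: Section 3.3 requires an identified donor before enrollment, and Section 5.2 requires fitness, transplant eligibility in the physician's opinion and a caregiver. The chi-square test is simple, valid and directed at the marginal difference, and it costs nothing if the factors do not matter. This is a secondary endpoint. The plan also has other views of the same question: time to transplant by log-rank in Section 3.3.2, and the rule in Section 17.5 on CPX-attributable failure to reach transplant.

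Most of this stands, and it limits the point to a conditional one of low severity. Two things remain. The inference that the factors matter is reasonable, because Section 17.2 already adjusts the survival analyses for them, death before transplant precludes it, and high-risk disease under Section 17.4 includes incomplete count recovery. And stratifying loses nothing material even if the inference is wrong (76.32% against 76.61% at OR 1, within simulation error).

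A reader might infer more than the documents support:

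- **That the test is undersized as a matter of fact.** This needs prognostic strata, and no stratum-specific transplant rates are given.
- **That close to ten points of power are lost.** One set of strong-strata assumptions does give 63.8% against 73.4% for 75% vs 56%. It goes with a size of 2.7%, which needs stratum rates of roughly 36%, 56%, 75% and 95%. Nothing in the documents suggests so wide a spread.
- **That the plan could miss a shortfall like 16 of 49.** Step 4 shows that either test would detect it.

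**Conclusion.** The point holds in conditional form. The transplantation proportions are the between-arm comparison in Section 17.2 that covers all randomized patients yet ignores the strata, and no reason is given. If both factors have odds ratios of 2 to 3 for reaching transplant, the true size is about 0.037 to 0.048 and about 1 to 3 points of power are given up. At an odds ratio of 5 on both factors, the figures are about 0.03 and 4 to 6 points (3.7 to 6.5 in the runs). At an odds ratio of 1 there is no loss.

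These figures rest on 65 per arm, an assumed two-sided alpha of 0.05, no continuity correction, and assumed transplant rates and odds ratios. Type I error is not inflated, so a significant result would stand, and the primary survival conclusion is untouched. Severity is low.

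**What to change.** In Sections 17.2 and 3.3.2, replace the chi-square test of the transplantation proportions (overall, day 60 and day 180) with a Cochran-Mantel-Haenszel test stratified on the two randomization factors as recorded at randomization. State that no continuity correction is used, and state the alpha. Report the stratum-weighted difference in proportions with a 95% confidence interval. That estimate is useful whatever the stratum effects turn out to be, since the plan now specifies only a test.

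The cost is a change of wording in each of the two sections. The strata are already recorded for the randomization, and no extra data or patients are needed.
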